#### b. VA Employees (Aim 3)

**Semi-Structured Stakeholder Interviews (50 minutes; see attached Stakeholder Interview Guide and *MOVE!+UP* video).** If the trial results are positive, semi-structured qualitative interviews will be conducted with VA Puget Sound employees to assess implementation barriers and facilitators. Interviews will last approximately 30-40 minutes, with the whole process taking approximately 40-50 minutes because participants will watch a 6-minute *MOVE!+UP* video describing *MOVE!+UP*'s key features and record their reactions on a provided notes sheet (see Stakeholder Interview Guide). Because stakeholders will represent different roles, certain questions will be tailored to their particular group. Participants also will be asked several basic demographic questions (e.g., profession, length of VA employment) to characterize the sample.

We will interview 15 clinical leaders and providers (stakeholders) from the two VA Puget Sound trial sites after 6-month trial outcomes are collected. Approximately 50-minute semi-structured interviews will be conducted by phone by our research coordinator, experienced in qualitative methods. Each interview will begin by viewing a 6-minute video to orient individuals to *MOVE!+UP*, including information on training, hiring, safety, and findings.

The interview guide will include open-ended questions about implementation challenges and facilitators, informed by the five CFIR domains: intervention characteristics, outer setting, inner setting, characteristics of individuals, and process. Specific salient constructs will be selected based on our experience in the trial, and additional questions will be tailored based on whether *MOVE!+UP* affected weight and PTSD. Interviews will be audio recorded and transcribed, with identifiable information redacted and stored separately from identifiers (in secure SFFX study folder).

### 5.6.a. Intervention Content and Delivery.

The curriculum for the 16 two-hour *MOVE!+UP* group sessions is in Table 6 below, with sessions 1-4 on basic weight loss, and 11-16 on maintenance. While CBT elements are included throughout, sessions 5-10 are dedicated to addressing PTSD-related barriers through challenging unhelpful thinking, problem-solving, promoting relationships and community engagement, and sleep hygiene. Facilitators use behavioral counseling skills such as motivational enhancement. All *MOVE!* materials were included, but many were modified to allow for PTSD content. (See attached Participant and Facilitator manuals). *MOVE!+UP* is led by a Veteran peer support counselor in recovery from mental illness, a model prioritized by OMHSP and VA Mission Act, and a psychologist who provides specialized PTSD care. *MOVE!+UP* pilot observations demonstrated value in the psychologist addressing PTSD-focused topics (e.g., sleep), and the peer counselor addressing those outlined in the peer support toolkit (e.g., social/community engagement, personal recovery). Facilitators alternate leading less specialized sections (e.g., weekly check-in). Two individual dietician visits are provided, and counseling calls are offered as needed.

Week	Content ( ***Content unique to MOVE!+UP in bold*** )
1: Orientation/ MOVE!+UP Overview	Energy balance, goal setting, behavioral strategies
2: Healthy Eating to Tip the Scale	Healthy plate, portion control, nutrition facts/labels
3: Physical Activity (PA) to Tip Scale	PA benefits & types (e.g., strength training); overcoming barriers
4: Eating Mindfully and Problem-Solving Barriers	Experiential mindful eating exercise , hunger/fullness scale, mindful eating tips, snack ideas, and problem-solving barriers
5: Coping w/ PTSD to Pursue Health	General coping, thought challenging , grocery shopping tips
6: Pursuing Wellness	Sleep assessment and improvement plan , finding joy, cooking
7: The Role of Relationships in	Benefits of relationships for health/PTSD; strategies for

Healthy Living I	enhancing relationships to improve health; meal planning
8: Relationships in Healthy Living II	Family/friend welcome; communication; relationships & PTSD
9: Community Engagement	Community engagement benefits/tips, problem-solving review
10: Health at any Size	Ways to enhance body image; thought challenging
11: Moving Toward Maintenance	Overcoming weight plateaus, adding challenge
12: Finesse your Food	Review strategies, e.g., healthy plate/nutrition facts
13: Stay Active!	PA motivators, personal values, long-term planning
14: Handling Slips and Setbacks	Relapse prevention, review of key diet tips. Thought challenging.
15/16: MOVE!+UP Progress Review	Review of progress and how to continue gains going forward.
1-16: CBT for PTSD ; set and track activity, diet, and weight goals; and experiential learning activities.	

**Table 6. Curriculum for *MOVE!+UP* Group Sessions**

Information was recorded in CPRS using standard procedures because these are clinical visits, likewise for *MOVE!* visits for the control condition.

1) *MOVE!+UP* sessions were offered by VVC and over the telephone using a backup conference line for those who may prefer to dial in and do not want to or cannot access VVC, dietician visits will be held by phone or VVC, and the community walk will be done individually during *MOVE!+UP* sessions in Veterans' own communities. In the highly unlikely case where VVC was not working, we had approval to switch to another VA-approved modality as listed in the Telehealth memorandum, titled "Use of Video Communication Technology Under COVID-19 (VIEWS 02576895)" and dated March 19, 2020.

2) Minor modifications were made to the facilitator and participant manual (see ALT Session 1 Facilitator Manual and ALT Participant Manual) from that used during the pilot to reflect information relevant to VVC delivery and recommendations appropriate during the pandemic and social distancing recommendations. Perhaps the biggest change is removing the family/friends invitation session so that it remains focused on social support but non-participants won't join (since that adds another layer of complexity for ensuring confidentiality). This is unlikely to have a major impact given no family or friends attended that session during the *MOVE!+UP* pilot.

3) We relied on phone, secure messaging, and VA's BHL Touch program for sharing clinical datapoints back and forth between facilitators and Veterans in *MOVE!+UP*, including weekly weighing, PTSD symptom assessments, diet/activity logging, photos of food labels and walking routes, and general support. Veterans were also given the option of sharing information like their weight during the group, just as is done in standard *MOVE!*. We attempted to set all study participants up with secure messaging after study enrollment to facilitate this important data sharing.

4) During each session, instead of the 40-minute facilitator-led group walk around the VA campus that was done during the pilot, participants were asked to walk in their own communities. Before the first session, they were asked to conduct walking safety audits in their community to ensure they have a safe

walk, using the walking audit form (see ALT Walking Audit). Those who weren't able to find a safe walking route in their immediate neighborhood for the walking component were encouraged to work with facilitators to identify other activities they could do during the 40 minutes of the walking component. We provided detailed instructions on how to walk safely, including how to handle emergencies, in the walking safety handout in the additional resources at the back of the participant manual. These safety promoting considerations are reviewed thoroughly in the first couple of sessions and then reiterated in brief at each subsequent session just prior to the walk

*MOVE!+UP* has numerous procedures for ensuring safety and confidentiality, and addressing other barriers to walk participation. Protocols for handling medical and mental health emergencies were developed with mental health leadership and physician Co-Is (see attached Safety Protocol).

5) We offered for Veterans to call into the backup conference line during the 40-minute walk in order to receive any additional support and build cohesion.

**Training and Quality Control.** The PI, a licensed clinical psychologist who developed *MOVE!+UP* and provided supervision in the pilot, trained and supervised peer and psychologist facilitators, with the goal of ensuring *MOVE!+UP* was delivered as intended and with high quality, optimizing *MOVE!+UP* benefits and validity and reproducibility of trial findings. Training and quality control procedures, used successfully in the *MOVE!+UP* pilot, incorporated elements used nationally by NCP to train and support *MOVE!* facilitators and by OMHSP to train peer support counselors and evidence-based PTSD treatment facilitators.

Initial Training and Ongoing Supervision. Prior to delivering *MOVE!+UP* to participants, facilitators built health behavior intervention skills and relevant knowledge, and familiarized themselves with *MOVE!+UP* content and structure. They reviewed the general structure and specific content for each session, as outlined in participant and facilitator manuals developed for our pilot. Facilitators participated in the online *MOVE!* Talent Management System (TMS) training, and NCP's nationally-disseminated TEACH for Success program, a one-day program that teaches evidence-based health coaching and motivational interviewing skills to VA primary care personnel. To promote safety and confidentiality, they took VA courses in basic life support; prevention and management of disruptive behavior; and information security; and were oriented to *MOVE!+UP* protocols for handling medical and mental health emergencies and identifying safety threats during the off-site walks. Peer support and psychologist facilitators role played in at least four audio-recorded sessions with volunteer staff acting as standard Veterans. Prior to delivering *MOVE!+UP* to RCT participants, facilitators must deliver sample *MOVE!+UP* content as intended and with high quality ( $\geq 80\%$  of components) using the standard rating forms we developed for each *MOVE!+UP* session during the *MOVE!+UP* pilot (see attached Fidelity form sample). Based on the *MOVE!+UP* pilot, we anticipated initial facilitator training would take a total of approximately 15 hours

over the course of two months. The Dietician received approximately two hours of brief training to orient them to *MOVE!+UP* logistics and equip them to address the needs of Veterans with PTSD. Once facilitators are trained, the PI listened to audio-recorded group sessions and rated fidelity with the standard forms created for the pilot, initially for at least 50% of sessions. Feedback was provided to facilitators during weekly supervision based on these ratings, and logistical issues were addressed. Study staff also listened to 20% of study sessions for fidelity. Fidelity ratings and qualitative input from supervision will be summarized and reported in study products.

Peer Counselor Training and Competency Assessment. Because there are unique training needs for this role, peer support counselors received additional training, guided by the VA peer support implementation toolkit. Peer counselors often facilitate groups and share their recovery experience but are not intended to replace or provide psychotherapy. Ongoing training and supervision focused on clarifying roles and responsibilities and the importance of maintaining boundaries and confidentiality. A national standard in VA, any new *MOVE!+UP* peer counselor completed 20 hours of online OMHSP training, after which they had to pass a general competency test. They also participated in the national bi-monthly training webinars hosted by OMHSP.

## 5.6.b. Data Analysis

**Power and Sample Size Calculations.** This study is powered on weight change at six months, comparing intervention and control conditions. We used formulas specified by Friedman et al. for use in clustered randomized controlled designs. Sample size was calculated for continuous outcomes and inflated to account for clustered randomization, using the inflation factor  $1 + (m - 1)\rho$  for cluster size  $m$  and intraclass correlation  $\rho$ , and attrition. Based on outcomes in prior weight loss trials, **we expect those in *MOVE!+UP* to lose 12 pounds on average, which would likely correspond to clinically meaningful weight loss (5% of baseline weight).** The specified expected weight loss is plausible, given *MOVE!+UP* pilot participants lost an average of 14 pounds, corresponding to 6% of baseline weight. We expect those in the control condition to achieve weight loss of 3.6 pounds on average consistent with Veterans with PTSD who participate in *MOVE!*, according to administrative data.

In the power calculation, the standard deviation of the outcome was assumed to be 13 based on previous findings. We calculated this value based on the marginal SD of 50 for baseline weight observed among Veterans with PTSD in *MOVE!*, between baseline and 6-month weight observed in the *MOVE!+UP* pilot (comparable to other weight loss effectiveness trials). Comparing these outcomes, an 8.4 pound difference in weight lost corresponds to prior behavioral weight loss trials and would yield a medium Cohen's  $d$  effect size of 0.65.

Table 7 displays the sample size required for varying cluster sizes *m* and intraclass correlation coefficients  $\rho$  assuming 90% power. The sample size of N=164 total Veterans (82 Veterans per treatment arm) chosen for this study assumes an ICC of 0.03, cluster size of 8 Veterans per randomized group, 90% power, a two-sided  $\alpha$  of 0.05, and a 6-month attrition rate of 25%, similar to MOVE!+UP pilot’s overall retention and a meta-analysis of missing data in weight loss RCTs. We will also be powered to detect a meaningful change in PTSD symptoms in the intervention condition at six months, aligned with the average PTSD symptom reduction of 18 (SD=12) observed among MOVE!+UP pilot cohort 5 participants and assuming a 9-point clinically meaningful reduction in the control condition.

**Table 7. Sample size considerations for MOVE!+UP hybrid type 1 trial**

ICC ( $\rho$ )	Cluster size (m)	Total Sample Size
0.05	10	196
0.05	8	182
0.03	10	172
0.03	8	164
0.01	10	148
0.01	8	144
Note: assumes a two-sided $\alpha$ 0.05, 90% power, a 12 – 3.6 = 8.4 lb difference in weight loss between groups, a weight change SD of 13, a 0.97 within-person correlation, and 25% attrition. The bolded row displays the selected parameters for the proposed study.		

**Quantitative Statistical Analysis Overview: Aims 1 and 2.** We will use intent-to-treat analyses to assess differences between intervention and control arms. We will use mixed effects models to account for clustering since participants in the intervention arm in the same enrollment cohort receive group treatment together. We will attempt to reduce attrition and missing data, which can lead to selection bias.

**Missing data.** In descriptive analyses, we will report summary statistics on proportion of patients with missing data in each of the study arms. We will report overall rates of missing data as well as specific rates for important variables such as study outcomes and baseline adjustment variables. We will provide descriptive statistics summarizing associations between available auxiliary variables and missingness in important model variables.

Methods for handling missing data in the primary analyses will be pre-specified and not influenced by the descriptive analyses described above. Missing data in the primary and secondary analyses will be accounted for through multiple imputation (MI) methods described below. Prior to multiple imputation, we will attempt to fill in missing baseline values of African-American race/ethnicity from the EHR.

Analyses of primary and secondary outcomes will account for missing data in outcome or baseline adjustment variables through Multiple Imputation (MI). We will perform MI using the Multiple Imputation by Chained Equations (MICE) method. MICE is a general purpose MI method that can handle missingness in variables of mixed data types (e.g. continuous and categorical) as well as

clustered data. Missing values will be imputed separately for each faux treatment group. MI will be performed using the outcome and baseline variables pre-specified for adjustment, and pre-specified auxiliary variables that are either likely associated with missingness and/or the outcome (gender, age, race, employment status, educational attainment, medication usage associated with a) substantial weight loss or b) substantial weight gain). We will create 50 imputed datasets, which will then be analyzed and combined according to Rubin’s rules for multiple imputation.

MICE requires specifying a statistical model to generate predictions for each variable with missingness. Table 9 lists the statistical models for each variable that will be used in the imputation procedure. Final imputed values will be based on the predictive mean matching approach, which can provide more plausible values when the distribution of a variable exhibits features such as bimodality or skewness.

Imputation Models

Variable Name	Variable Type	Statistical Model for MICE procedure	Rationale for inclusion
6-month Weight	Continuous	Linear regression	Outcome being imputed
Baseline Weight	Continuous	Linear regression	Typically associated with outcome
African-American race/ethnicity	Binary	Logistic regression	Typically associated with outcome and with missingness in a prior WL trial among Veterans
Employment status	Categorical	Multinomial regression	Associated with missingness in a prior WL trial among Veterans
Educational achievement	Categorical	Multinomial regression	Associated with missingness in a prior WL trial

 Citation: <https://www.ncbi.nlm.nih.gov/pmc/articles/PMC6408317/>

			among Veterans
Age	Continuous	Linear regression	Associated with missingness in a prior WL trial among Veterans
Gender	Categorical	Multinomial regression	Typically associated with outcome and was associated with missingness in a prior WL trial among Veterans
Weight management medication usage in the 6 mos following enrollment (Yes vs. no)	Binary	Logistic regression	Typically associated with outcome
Weight gain meds in the 6 mos following enrollment (Yes vs. no)	Binary	Logistic regression	Typically associated with outcome

**References:** Prior WL trial among Veterans: <https://jamanetwork.com/journals/jama/fullarticle/2799407>; [name] will add references for gender, Af-Am race

MICE requires specifying a statistical model to generate predictions for each variable with missingness. Final imputed values will be based on the predictive mean matching approach, which can provide more plausible values when the distribution of a variable exhibits features such as bimodality or skewness.

As suggested by Althouse, in addition to reporting statistical significance based on an alpha of .05, we will report effect sizes and confidence intervals so readers can determine whether the effects warrant policy and clinical practice change. Also recommended by Althouse, although this study includes a single primary outcome for determining effectiveness, therefore reducing likelihood of Type I error, we will also report the actual p-value for all analyses, which would allow a reader to adjust for multiple comparisons. We will report summary statistics for baseline covariates and outcomes (means, standard deviations, and quartiles for continuous variables; frequencies and percentages for binary variables) by randomized group, including the proportion achieving clinically meaningful weight loss ( $\geq$  5% baseline weight).

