**Note: Aim 3 analyses are not covered in this statistical analysis plan.**

Table 1. Statistical Models

Analysis	Outcome(s)	Independent Variables
Primary analysis	6-month absolute weight change from baseline (pounds)	Binary treatment indicator  Baseline weight  Binary African-American race indicator
Secondary analyses	1. 6-month absolute change in PTSD symptoms from baseline 2. 12-month absolute change in PTSD symptoms from baseline 3. 12-month absolute weight change from baseline (pounds)	Binary treatment indicator  Baseline outcome  Binary African-American indicator (weight analysis only)
Exploratory analyses	6-month absolute change from baseline in: 
 
Diet quality
 
Eating habits
 
Night eating
 
Emotional eating
 
Average MVPA and average LMVPA (adjust for total # of valid days at baseline and 6 months)
 
Social support – Diet
 
Social discouragement – Diet
 
Social support – physical activity
 
Social discouragement – physical activity
 
Insomnia Severity Index (ISI)
 
Depression symptoms
 
Internalized Weight Bias
 
	Binary treatment indicator  Baseline outcome

 All models account for clustering through the inclusion of a random intercept for group treatment cluster.

Analysis	Outcome(s)	Independent Variables
Exploratory Analyses	Binge eating at 6 months	Binary treatment indicator
Sensitivity analyses:  adjusting for prior weight loss treatment	1. 6-month absolute weight change from baseline (pounds) 2. 12-month absolute weight change from baseline (pounds)	Binary treatment indicator  Baseline outcome  Binary African-American indicator  Total number of MOVE! visits 12 months prior to baseline  Binary indicator of prescription weight loss medications at baseline
Sensitivity analyses:  adjusting for prior mental health treatment	1. 6-month absolute change in PTSD symptoms from baseline 2. 12-month absolute change in PTSD symptoms from baseline	Binary treatment indicator  Baseline outcome  Total number of mental health visits 12 months prior to baseline, per EHR  Number of PTSD visits in the prior year  Binary indicator of PTSD medications in the last year

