Sensitivity analyses:  Including auxiliary variables to assess impact of missing data	1. 6-month absolute weight change from baseline (pounds) 2.	Binary treatment indicator  Baseline outcome  Binary African-American indicator (weight analyses only)  Auxiliary variables discussed in the Handling of Missing Data section. Plus those that appeared possibly associated with missingness on 6-month weight in descriptive comparisons.
Sensitivity: bariatric surgery	1. 6-month absolute weight change from baseline (pounds) 2. 12-month absolute weight change	Binary treatment indicator

Analysis	Outcome(s)	Independent Variables
influence	from baseline (pounds)	
Baseline outcome
 
Binary African-American indicator (weight analyses only)
 
Remove veteran outcome with bariatric surgery. However no one had bariatric surgery during the study period so this analysis is not being conducted.

Sensitivity analysis: examine differences in utilization across tx conditions and the influence of these factors on weight loss outcome.	
 
1. 6-month absolute weight change from baseline (pounds)
 
2. 12-month absolute weight change from baseline (pounds)
 
3.
 
	
Binary treatment indicator
 
Baseline outcome
 
Binary African-American indicator (weight analyses only)
 
-Binary indicator of prescription weight loss medications from baseline to 6 and 12 months reported in EHR and/or self report
 
-binary indicator of non-MOVE! +UP/MOVE! weight management care (i.e., any self-reported non-Va program, dietician visits TeleMOVE!). Will not include self-reported use of websites, Fitbits etc.
 
If the pattern of results changes from what was found in the primary analysis, we would pursue a formal mediation analysis.

Sensitivity analysis: If we see substantial issues with the q-q plots when the primary analysis is	
 
1. 6-month log-transformed weight change from baseline (pounds)
 
1.
 
	
Binary treatment indicator
 
Baseline outcome
 
Binary African-American indicator (weight analyses only)

Analysis	Outcome(s)	Independent Variables
run, we will do a sensitivity analysis with a log-transformed outcome		

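### The listed imputation model leaves out covariates of some sensitivity models, so on the imputed data those models would understate how far adjustment moves the treatment effect

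*Combined protocol and SAP*

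**What the plan says.** All of this is in section 5.6.b of the combined protocol and SAP.

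- **Scope of imputation (Missing data).** "Analyses of primary and secondary outcomes will account for missing data in outcome or baseline adjustment variables through Multiple Imputation (MI"). Sensitivity analyses are not named, and no other method for missing outcomes is given for them.
- **Content of the imputation model.** "MI will be performed using the outcome and baseline variables pre-specified for adjustment, and pre-specified auxiliary variables". The Imputation Models table then lists 6-month weight, baseline weight, African-American race/ethnicity, employment, education, age, gender, and use of weight-loss and of weight-gain medication in the 6 months after enrollment. Imputation is done separately by group, which I take to mean by arm.
- **Prior weight-loss treatment (Table 1, Statistical Models).** These models for 6- and 12-month weight add "Total number of MOVE! visits 12 months prior to baseline" and "Binary indicator of prescription weight loss medications at baseline".
- **Prior mental health treatment (same table).** These models for 6- and 12-month PTSD symptoms add mental health visits in the year before baseline, "Number of PTSD visits in the prior year" and PTSD medication.
- **Utilization (same table).** These weight models add weight-loss medication after baseline and an indicator of weight care outside the study programs. The row ends: "If the pattern of results changes from what was found in the primary analysis, we would pursue a formal mediation analysis".

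**The concern.** A covariate in the analysis model should also be in the model that imputes the outcome. If it is not, outcomes are imputed as if the covariate mattered only through the variables that are listed. Analysing observed and imputed outcomes together then gives a coefficient that is too close to zero, and adding the covariate moves the treatment effect less than it should.

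The direction of this bias is known. It favours the conclusion that adjustment changes nothing, which is what these analyses are meant to test. In the utilization row, the decision to go on to a mediation analysis depends on whether adjustment changes the picture, so dilution could keep that step from being triggered.

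**Working it through.** **Inputs.** From the power section of 5.6.b: difference 12 − 3.6 = 8.4 lb, SD of change 13 lb, two-sided alpha 0.05, power 90%, ICC 0.03, cluster size 8, 25% attrition at 6 months. From the abstract: 174 randomised, so 87 per arm if 1:1. The documents give no observed missing rates. Covariate strength, imbalance and correlation below are assumptions.

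**1. The plan's own figure.** Per arm, 2 × [13 × (1.960 + 1.282) / 8.4]² = 50.3. Multiply by 1 + 7 × 0.03 = 1.21 and divide by 0.75: 81.2, rounded up to 82, or 164 in total. This matches Table 7, so 25% is the missing fraction the design allows for. The plan gives no figure for dilution in the sensitivity models.

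**2. Which models are affected.**

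| Sensitivity analysis | Added covariates in the imputation table? |
|---|---|
| Prior weight-loss treatment | Neither |
| Prior mental health treatment | None; PCL-5 also has no imputation model |
| Utilization, 6 months | Medication yes; outside weight care no |
| Utilization, 12 months | Neither; 12-month weight also has no imputation model |
| Auxiliary variables | Named ones yes; any added after the descriptive comparisons no |
| Log-transformed outcome | No covariate added |
| Bariatric surgery | Not being run |

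**3. Expected dilution.** Let a covariate have coefficient γ and between-arm imbalance d, and let a fraction π of outcomes be missing at random. Full data give a shift of γd on adjustment. If the covariate is unrelated to the imputation variables, the imputed share contributes nothing to its coefficient, so the coefficient becomes (1 − π)γ and the shift (1 − π)γd. If it has correlation r with a listed variable, the factor becomes (1 − π) + πr². At π = 0.25 this is 0.75 for r = 0, 0.75 + 0.25 × 0.25 = 0.81 for r = 0.5, and 0.75 + 0.25 × 0.81 = 0.95 for r = 0.9.

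**4. Simulation.** N = 174, predictive mean matching by arm, ICC 0.03, 10 imputations, 400 replicates, least-squares point estimates. The covariate explains 10% of variance and differs by 0.3 SD between arms.

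| Setting | Shift relative to full data |
|---|---|
| 10% missing | 0.90 |
| 15% missing | 0.85 |
| 25% missing | 0.76 (0.93 vs 1.24 lb) |
| 35% missing | 0.63 |
| 25%, r = 0.5 / 0.7 / 0.9 with a listed variable | 0.79 / 0.85 / 0.91 |
| 25%, missingness depends on the covariate | 0.72 |
| 25%, covariate included in the imputation | 0.97 (1.20 vs 1.24 lb) |

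The ratios for correlated covariates fall slightly below the formula because imputation that includes the covariate itself recovers about 97%.

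**5. Size in pounds.**

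- *Chance imbalance, continuous covariate.* One standard error at 82 per arm is √(2/82) = 0.156 SD. The simulated shift is 0.48 instead of 0.65 lb, a loss of 0.17 lb. At 0.3 SD the loss is 1.24 − 0.93 = 0.31 lb.
- *Chance imbalance, binary covariate, 17.5% prevalence.* One standard error is √(0.175 × 0.825 × 2/87) = 0.058. A −10 lb covariate then shifts the effect by 0.58 lb, of which 25% is 0.14 lb. A −6 lb covariate loses about 0.09 lb.
- *Stress case.* Prevalence 10% in controls and 25% in MOVE!+UP, covariate worth −10 lb (separate simulation, normal-model imputation by arm, no clustering, 600 replicates): coefficient −7.4 when omitted against −10.2 when included; shift 1.11 lb against 1.48 lb with complete data, a loss of 0.37 lb. For a baseline covariate this gap is 0.15/0.058 = 2.6 standard errors.
- *Yardstick.* The treatment effect's standard error at 25% attrition is 13 × √(2/65.25) = 2.3 lb, or 2.3 × √1.21 = 2.5 lb with clustering.

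**The case against.** **Use of the imputed datasets is inferred.** The plan assigns imputation to the primary and secondary analyses and labels the sensitivity analyses separately. This stands: the dilution arises only if the same imputed datasets are reused. But no other method is offered and the sensitivity models analyse those same outcomes. If they were instead run on complete cases, comparing them with the imputed primary result would change the covariates and the missing-data handling at once, so the plan needs a statement either way.

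**The table may cover only the primary outcome.** It names 6-month weight alone. This stands for PTSD and 12-month weight: the gap there is a missing imputation model rather than a covariate left out of a stated one. One could also read the phrase about pre-specified adjustment variables as taking in the sensitivity covariates, but the table for 6-month weight does not list them.

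**The effect is small.** This stands for baseline covariates. Randomisation keeps imbalance near chance, and even the stress case is under 0.2 standard errors of the treatment effect (0.37/2.3 = 0.16).

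**The outside-care indicator is partly self-reported.** Participants lost to follow-up may lack it too, whereas the simulations assume the covariate is fully observed. This stands, and means that adding a predictor is not enough for that variable.

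**Stronger readings.** A reader might infer that every sensitivity analysis is diluted to three-quarters. The coverage table in the working shows otherwise, and three-quarters rests on a planning rate. A reader might also infer that imputed outcomes carry no relation at all to the omitted covariates. Some relation survives through listed variables; baseline weight-loss medication, for example, plausibly tracks use after enrollment, which is listed.

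**Conclusion.** The point holds for the prior-weight-loss-treatment models, for the part of the utilization model not covered by the imputation table, and for any variable added late to the missing-data analysis. It extends to the prior-mental-health models, where no imputation model is stated. If these run on the planned imputed datasets, the shift in the treatment effect is understated by roughly the missing fraction: about a quarter at 25% attrition and a tenth at 10%.

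For baseline covariates I would expect a loss of about 0.1 to 0.3 lb against a design effect of 8.4 lb. No figure in PCL-5 points was derived. The utilization model could be hit harder: its covariates arise after randomisation, so the arms may differ for reasons other than chance. Section 5.1 lets controls use other MOVE! modalities, and section 5.5 tells MOVE!+UP participants to stay out of MOVE!.

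The primary analysis is untouched, since both of its covariates are in the imputation model. So are the log-transform analysis, the bariatric analysis that is not being run, and the named auxiliaries in the missing-data analysis. The documents therefore do not support reading this as a threat to the main result. Severity is minor.

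**What to change.** - State how missing outcomes are handled in each sensitivity analysis.
- Add each sensitivity covariate to the imputation model for the outcome concerned, or re-impute for each sensitivity model with its covariates included. For weight these are prior-year MOVE! visits, baseline weight-loss medication, outside weight care and, for the 12-month outcome, weight-loss medication to 12 months. For PTSD they are prior-year mental health visits, PTSD visits and PTSD medication.
- Treat any variable added after the descriptive comparisons the same way. Re-imputing for that analysis alone suits it best, because the plan says those comparisons will not influence missing-data handling in the primary analysis.
- Write out imputation models for PCL-5 and 12-month weight on the same basis.
- Impute the outside-care indicator where it is itself missing.

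The cost is SAP wording and some code; the models already require these variables. The downside is a few more predictors in a modest by-arm sample of about 87. Re-imputing per sensitivity model avoids carrying all of them at once and leaves the primary imputation as specified.
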